Title page

Protocol Title: Pseudoephedrine Prophylaxis for Prevention of Middle Ear Barotrauma in Hyperbaric Oxygen Therapy NCT Study No.: NCT04332211

Principal Investigator: [name] Revised Sudafed Study Protocol Date: 1/17/22

Protocol

The initial study design employed a 1:1 pseudoephedrine to placebo ratio. At exactly half enrollment (42 out of 84) the research team recognized that the capsule prepared requires 15 minutes to be dissolved, in addition to the 20-30 minutes it takes for the pseudoephedrine tablet to be absorbed and take effect. Therefore, the following two changes have been applied to the protocol: 1. The study capsule will be administered 45 minutes prior to initiation of hyperbaric oxygen therapy; 2. The ratio of pseudoephedrine to placebo will be changed to 2:1 starting with enrollment #43; The total number of enrollments will be increased from 84 to 105. (Because the participants who received the Sudafed tablet did not have enough time for the study capsule and tablet to be digested and take effect we can not use their data for a reliable comparison of Sudafed to placebo. To reiterate, we have enrolled 21 with placebo, and 21 with badly-timed Sudafed. Overall, we need 42 with placebo and 42 with well-timed Sudafed based on our power calculation. Thus, we need another 21 (placebo) and 42 (well-timed Sudafed). This will require us to enroll another 63 patients with a 2:1 ratio. Thus we will need to increase the total number of participants we enroll for the protocol because the initial 21 with badly-timed Sudafed can not be used in the direct comparison calculations. In summary, in order to increase the number of Sudafed enrolled patients, we plan to change the enrollment ratio starting with #43 to 2 (Sudafed) to 1 (placebo). To reach statistical significance, based on our power calculation, we will need to increase our enrollment to a total of 105 (from initial 84) with the next 63 capsules packaged in the 2 Sudafed to 1 placebo ratio.)

Additionally, given the December 2021 RNI IRB recommendations, [name] (PI) will be the only study member who reviews and sings the eligibility criteria checklist for each enrolled participant (this was the case previously, but now is officially in the protocol)

Research Design and Methods

The study will employ a prospective randomized double-blind placebo control study design (enrollment ratio 1:1 – this ratio is changed to 2 Sudafed to 1 placebo starting enrollment #43 given the explanation above) to compare whether pseudoephedrine is more effective than placebo in preventing barotrauma during HBOT.

Setting: The study will take place in the UMMC Center for Hyperbaric and Dive Medicine.

Subjects: Convenience sample of patients undergoing their first HBOT.

Inclusion criteria: New patient requiring HBOT (either inpatient or outpatient) Age greater than or equal to 18 years and less than 80 years Fluent in English Full decision capacity Able and medically cleared to swallow a pill

Exclusion criteria:

Enrollment would delay hyperbaric therapy more than 30 minutes in patients with emergent indications (example: CRAO, CO, AGE) Contraindication to pseudoephedrine (MAOI use, pregnancy, glaucoma, heart disease, allergy to drug class) SBP >160 DBP > 90 HR >100 Decongestant/antihistamine/pseudoephedrine/nasal steroid/oxymetazoline use within 12 hours. Prisoner Intubated Unable take PO meds

Enrollment:

Trained research assistants will approach patients scheduled for their initial HBOT. If the patient is interested in participation, informed consent will be obtained. A copy of the informed consent will be given to the patient, and the signature page will be collected and kept in a secure location. Enrolled patients will be de-identified and assigned a consecutive study number starting with the number one. A record on the total number of potential eligible participants approached will also be kept. In order to confirm decision making capacity, the patient will be asked the following three questions prior to signing the consent form: 1. Why are we doing this study?; 2. What medication are we testing in this study?; 3. Who can you contact if you have further questions about the study? If the patients are able to answer these questions and the attending hyperbaric physician has them sign an informed consent form for the scheduled hyperbaric therapy, then they are deemed competent to be enrolled in the study. In order to prevent enrolling pregnant patients, the attending hyperbaric physician will be asked to check the result of the pregnancy test. If positive, or not available in a female patient of child bearing age, the patient will be excluded from the study. The PI will be the only study member who will review and sign the eligibility criteria for each enrolled participant.

Protocol:

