The sample size of 42 was calculated for enrollment into each group (use of pseudoephedrine, no use of rescue pseudoephedrine) to detect a significant difference in pain score between the treated and untreated groups. We use the standard Alpha=0.05, and power of 80%. This calculation was based on the incidence of barotrauma in placebo groups based on prior publications in scuba divers (32%). The incidence in pseudoephedrine treated group was 8%.

Sample Size	
Group 1	42
Group 2	42
Total	84
Study Parameters	
Incidence, group 1	32%

Incidence, group 2	8%
Alpha	0.05
Beta	0.2
Power	0.8

We will screen 90 patients (5% oversample) to obtain the required subjects in each group.

The primary outcome variable will be the frequency of severe pain and need for oxymetazoline rescue therapy, between the two groups. These frequencies will be compared using chi-square or Fisher's exact test, as appropriate. We will calculate 95% confidence intervals for the difference in frequencies between groups using normal binomial approximation.

Model building will be based on the results of the univariate analysis of independent and outcome variables. During model building, we will also test variables in a stepwise fashion into the model to identify confounders and effect modifiers. We will then use logistic regression analysis to build the final model between our independent variables to our dependent or outcomes variable.

Timeline:

IRB application will be completed by mid-April 2020.

Medical student and RN research assistant will complete CITI training and be added to the IRB protocol by May 2020

UMMC Investigational drug pharmacy will be notified about the need for manufacturing and deidentification of placebo and pseudoephedrine by mid-April 2020.

Study will be registered with ClinicalTrials.gov by May 2020.

Patient enrollment will begin by mid May 2020 (end of first year of medical school)

We anticipate reaching goal of 84 enrolled patients prior to November 2020.

Data analysis and abstract will be complete by February 2021.

Manuscript will be submitted to Undersea and Hyperbaric Medicine Journal by March 2021.

Limitations:

Given the small sample size, it is possible that some factors, measured or unmeasured, that may affect ear pain or request for rescue therapy will randomly differ between pseudoephedrine and placebo groups. Such factors may bias the study.

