Our comparisons were based on our primary outcome measures (pain ratings, Teed scores, and oxymetazoline rescue therapy) between placebo and pseudoephedrine. Our sample size, based on power 0.8, significance 0.05, and effect size 8% versus 32%, was 42 patients in each group. The effect size was based on barotrauma measured in SCUBA divers [10]. Initial allocation was 1:1, but by the 42nd enrollment, we learned that the capsules prepared by the investigational drug pharmacy required additional dissolution time, necessitating a 45-minute wait rather than the original 30-minute protocol. Because of inadequate time for drug effect, patients assigned pseudoephedrine up to that point were not considered for the primary outcome comparison. Thus, we subsequently changed our allocation to 2:1 to increase the number receiving pseudoephedrine, starting with subject #43. This increased our total enrollment from 84 to 105.

For comparisons of placebo versus pseudoephedrine, we used only subjects with pseudoephedrine ingested at least 45 minutes before HBO2 treatment. We used data from subjects provided pseudoephedrine less than 45 minutes before treatment only for estimates of the incidence of complications of HBO2 treatment.

We compared frequencies of primary outcome measures using chi-square or Fisher's exact test, as appropriate. We calculated 95% confidence intervals for the difference in frequencies between categories using normal binomial approximation. We compared ordinal variables using the Wilcoxon rank sum test.

We used logistic regression to adjust for potential confounding by baseline variables (age, sex, HBO2 pressure, history of obstruction, sinus disease, smoking, and inpatient status). We used backward selection, aiming for a precise and unbiased estimate of the pseudoephedrine effect. We removed only variables whose removal would not change this estimate by >10% or increase the standard error by >20%.

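### Half of the placebo controls were randomised before anyone could receive the timed regimen; the stable-placebo-rate assumption is not stated and no concurrent #43-105 comparison is given

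*Combined protocol and SAP*

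**What the plan says.** The opening Protocol section (revision dated 1/17/22) reports that #1-42 were allocated 1:1, giving 21 placebo patients and 21 pseudoephedrine patients whose dose was judged badly timed. From #43 allocation is 2:1. The early placebo patients count toward the required 42 per group: "Thus, we need another 21 (placebo) and 42 (well-timed Sudafed".

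The Statistical analysis section of Materials and Methods (taken from an accepted manuscript) confirms the exclusion: "patients assigned pseudoephedrine up to that point were not considered for the primary outcome comparison". The timing condition for entering the comparison applies to pseudoephedrine only, so early placebo patients stay in.

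The analyses in that section are:
- Tests: "We compared frequencies of primary outcome measures using chi-square or Fisher's exact test, as appropriate", with the Wilcoxon rank sum test for ordinal variables.
- Interval: "We calculated 95% confidence intervals for the difference in frequencies between categories using normal binomial approximation".
- Logistic regression on seven candidate covariates: "age, sex, HBO2 pressure, history of obstruction, sinus disease, smoking, and inpatient status". On selection: "We used backward selection, aiming for a precise and unbiased estimate of the pseudoephedrine effect". A variable is removed only if this changes the drug estimate by no more than 10% and raises its standard error by no more than 20%.

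The protocol's Limitations cover chance imbalance, pain-scale bias and generalisability. They do not mention enrolment period.

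**The concern.** Randomisation protects comparisons between patients who could have been assigned to either of the regimens compared. From #43 on that holds: planned 42 pseudoephedrine v 21 placebo. The other 21 placebo patients were randomised against a regimen that has been dropped from the comparison, so for this purpose they are earlier controls from the same centre.

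Using them is legitimate if the placebo event rate was the same before and after #43. That assumption is not stated in the documents. The tests are not stratified by period, period is not among the seven covariates, and no analysis is limited to #43-105. Enrolment of a convenience sample ran from May 2021 to July 2023, and the outcomes are a pain rating, a graded otoscopic score and the need for rescue spray. A change in patients, staff or scoring over that time could be read as a drug effect or could hide one, and the analyses described would not show it.

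**Working it through.** **Inputs.** Alpha 0.05 (two-sided assumed, as sidedness is not stated), power 80%, 32% v 8% and 42 per group come from the protocol's Statistical analysis section. The split of 21 early placebo, 21 late placebo and 42 late pseudoephedrine comes from the opening Protocol section. Drift sizes and the 20% base rate are assumptions, since the documents give no placebo rates by period. The 32% and 8% are borrowed: "The effect size was based on barotrauma measured in SCUBA divers".

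**The plan's own figure.** With mean rate 0.20, n per group = [1.96·√(2·0.20·0.80) + 0.842·√(0.32·0.68 + 0.08·0.92)]² / 0.24² = (1.109 + 0.454)² / 0.0576 ≈ 42.4, so 43. At 42 per group, normal-approximation power is 79.6%. The stated 42 and 80% are reproduced.

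**Bias.** Let p be the late placebo rate and p + d the early rate. The pooled placebo rate is expected to be [21(p + d) + 21p] / 42 = p + d/2. The unadjusted risk difference is therefore off by d/2: 5 points for d = 10, 10 points for d = 20.

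**Type I error.** Exact binomial enumeration with no drug effect (pseudoephedrine rate = p), pooled 42 v 42:

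| Early placebo rate | Chi-square, p = 20% / 32% | Fisher, p = 20% / 32% |
|---|---|---|
| same | 5.2% / 5.1% | 2.9% / 3.0% |
| 10 points higher | 8.6% / 8.0% | 5.4% / 5.0% |
| 20 points higher | 18.4% / 16.5% | 13.0% / 11.4% |

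If Fisher is used only when an expected count is below 5 (an assumed reading of the plan's phrase on choosing the test), it would be chosen in under 2% of 42 v 42 tables in these scenarios. The chi-square column is then the relevant one.

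**Interval.** The planned normal-approximation 95% interval covers the true concurrent difference in 94-95% of trials without drift, 90-92% at +10 points and 77-83% at +20 points. The ranges span no effect at 20%, no effect at 32%, and a true 8% v 32%.

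**Power, pooled, at 32% v 8%.** Chi-square power is 82.4% without drift, 66.4% if the early rate is 10 points lower and 92.3% if 10 points higher. Drift moves it in either direction.

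**Concurrent comparison, 42 v 21, at 32% v 8%.**
- Power is 62.9% (Fisher) to 66.4% (chi-square), against 75.1% to 82.4% for 42 v 42.
- With the test chosen by expected counts, Fisher is used in 94% of 42 v 21 tables and 1% of 42 v 42 tables. Power is then 63.0% v 82.2%, a loss of 19 points.
- Interval half-width is 1.96·√(0.32·0.68/21 + 0.08·0.92/42) = 21.6 points, against 1.96·√(0.32·0.68/42 + 0.08·0.92/42) = 16.3 points pooled.
- Coverage is 93-94% whatever the drift.

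**Mean squared error.** Leaving out the pseudoephedrine term common to both, the pooled estimate is better when d²/4 + [(p + d)(1 − p − d) + p(1 − p)]/84 < p(1 − p)/21. At p = 20% this holds for d between −14.2 and +11.2 points; at p = 32%, between −15.7 and +13.9 points.

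**Placebo check, 21 v 21.** Power to detect a 20-point drift is 25% chi-square / 15% Fisher (32% v 52%), 36% / 24% (32% v 12%) and 31% / 19% (20% v 40%). The 95% half-width is 24 points at 20% and 28 points at 32%.

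**The case against.** The strongest reply is that the pooling is open and reasoned, and that large drift is not especially likely. This was one centre with blinded patients and staff. Materials and Methods describes a constant compression rate, standardised education on ear equalisation, and one physician doing both otoscopic gradings for each patient. Nothing in the documents suggests that a longer wait after a placebo capsule would change ear outcomes. All of this stands, and it makes 10- or 20-point drift an illustration rather than an expectation. It does not establish stability.

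The logistic model also helps. Drift caused by measured case-mix can be adjusted for, so the half-size bias applies to the unadjusted risk difference. A reader might infer that backward selection could discard this protection. The stated rule does not support that: a covariate whose removal moves the drug estimate by more than 10% is kept. What remains is drift from unmeasured causes, which no listed covariate captures.

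The pooled estimate is also the more accurate one for modest drift, by the mean squared error limits above. That is a good reason to keep it, but not to leave its assumption unstated.

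Finally, only the manuscript's methods are supplied. Its results and discussion may address the point, so not stated here means not in these documents. The protocol's Limitations do mention unmeasured factors, but as random differences between groups rather than as a period effect.

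**Conclusion.** The concern holds as a gap in validity and transparency. Half of the controls (21/42) lie outside the concurrently randomised comparison, and the documents neither state the assumption that justifies them nor give an analysis that would let a reader judge it. If the placebo rate was stable, pooling does no harm. If the early rate was 10 points higher, the unadjusted estimate is off by 5 points and chi-square type I error is about 8-9%; at 20 points, 10 points and about 17-18%. These sizes rest on assumed drift, base rates of 20% or 32%, and the planned 21/21 split.

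Two stronger readings should be resisted. One is that the result is biased; no drift is shown, so this does not follow. The other is that the power calculation is wrong or that pooling necessarily costs power. The calculation reproduces, and drift can raise rejection probability as well as lower it. Power for the pain, otoscopic and rescue outcomes themselves is unknown, because the planning rates are barotrauma in divers.

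**What to change.** 1. Keep the pooled 42 v 42 result. Label it as including non-concurrent controls, and state that it assumes the same placebo rate before and after #43.
2. Beside it, report all patients from #43 as randomised (planned 42 v 21) for every primary outcome, including the Wilcoxon comparisons of ordinal variables. As the methods come from an accepted manuscript, call this a post hoc sensitivity analysis.
3. Tabulate placebo outcomes for #1-42 and #43-105 with a 95% interval for the difference. Do not read a non-significant difference as proof of no drift.
4. State the downsides. The concurrent comparison gives up 19 points of power at the diver rates when the test is chosen by expected counts. Its interval is about 22 rather than 16 points either side and slightly under-covers. The placebo check has only 15-36% power for a 20-point drift.

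The cost is one further analysis, a small table and a few sentences, all from data already collected.

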The sample size of 42 was calculated for enrollment into each group (use of pseudoephedrine, no use of rescue pseudoephedrine) to detect a significant difference in pain score between the treated and untreated groups. We use the standard Alpha=0.05, and power of 80%. This calculation was based on the incidence of barotrauma in placebo groups based on prior publications in scuba divers (32%). The incidence in pseudoephedrine treated group was 8%.

Sample Size	
Group 1	42
Group 2	42
Total	84
Study Parameters	
Incidence, group 1	32%

Incidence, group 2	8%
Alpha	0.05
Beta	0.2
Power	0.8

We will screen 90 patients (5% oversample) to obtain the required subjects in each group.

The primary outcome variable will be the frequency of severe pain and need for oxymetazoline rescue therapy, between the two groups. These frequencies will be compared using chi-square or Fisher's exact test, as appropriate. We will calculate 95% confidence intervals for the difference in frequencies between groups using normal binomial approximation.

Model building will be based on the results of the univariate analysis of independent and outcome variables. During model building, we will also test variables in a stepwise fashion into the model to identify confounders and effect modifiers. We will then use logistic regression analysis to build the final model between our independent variables to our dependent or outcomes variable.

Timeline:

IRB application will be completed by mid-April 2020.

Medical student and RN research assistant will complete CITI training and be added to the IRB protocol by May 2020

UMMC Investigational drug pharmacy will be notified about the need for manufacturing and deidentification of placebo and pseudoephedrine by mid-April 2020.

Study will be registered with ClinicalTrials.gov by May 2020.

Patient enrollment will begin by mid May 2020 (end of first year of medical school)

We anticipate reaching goal of 84 enrolled patients prior to November 2020.

Data analysis and abstract will be complete by February 2021.

Manuscript will be submitted to Undersea and Hyperbaric Medicine Journal by March 2021.

Limitations:

Given the small sample size, it is possible that some factors, measured or unmeasured, that may affect ear pain or request for rescue therapy will randomly differ between pseudoephedrine and placebo groups. Such factors may bias the study.

There is inherent bias in the pain scale. This is addressed by also examining the patient's tympanic membrane and asking pain score before the patient's treatment starts. Finally our results may not be generalizable given the small sample size and single center patient cohort.

Human Subjects

New patients requiring HBOT who will be approached about enrollment based on inclusion/exclusion criteria. We are avoiding vulnerable study populations such as children and prisoners. Informed consent will be obtained by trained study team members.

We will de-identify the enrolled subjects. We are only asking information about age, sex, smoking history, sinus disease, airplane flight history and current nasal congestion. We will also document limited physical exams findings including heart rate, blood pressure and tympanic membrane evaluation. None of these data points will provide any identifiers.

With respect to the intervention, pseudoephedrine is an over the counter widely used medication. We have ensured that through our exclusion criteria, we will not any significant cardiovascular risk to our enrolled patients.

MATERIALS AND METHODS (from accepted manuscript for Journal of Undersea and Hyperbaric Medicine)

Study design

This was a prospective randomized, double-blind, placebo-controlled trial of pseudoephedrine prophylaxis in patients undergoing their first treatment of HBO2 treatment. The study was conducted between May 2021 and July 2023 in the multiplace HBO2 facility at the University of Maryland Medical Center. The study was approved by our institutional research board and registered with ClinicalTrials.gov (NCT04332211).

Enrollment

A convenience sample of new patients requiring HBO2 treatment (inpatient and outpatient) were approached about enrollment at the time of initial consultation. We included English-speaking patients between the ages of 18 and 80 years. We excluded patients with contraindications to pseudoephedrine (monoamine oxidase inhibitor use, pregnancy, glaucoma, heart disease, allergy), hypertension (systolic blood pressure >160mmHg, diastolic blood pressure >90mmHg), tachycardia (pulse >100/minute), decongestant/antihistamine/nasal steroid use within 12 hours, prisoners, intubated patients, those unable to swallow a pill, history of hyperbaric treatment, SCUBA divers, those with pressure-equalizing tubes, and patients requiring emergent treatment.

Protocol

Consenting patients enrolled in the study ingested a study pill at least 45 minutes, and no longer than 120 minutes, before starting their first multiplace treatment. The pill contained either 60 mg of pseudoephedrine or a placebo, prepared and de-identified by the hospital investigational drug pharmacy. Patients, investigators, and hyperbaric department staff were blinded to the intervention medication. Before treatment, patients self-reported age, sex, whether they smoked tobacco within 24 hours, whether they had acute sinus congestion and any history of chronic sinus disease. We also measured their heart rate and blood pressure. Pre-treatment ear pain ratings were collected using a verbal numerical scale (0=no pain, 10=worst pain imaginable), and Teed scores (0 = normal; 1 = erythema of TM; 2 = erythema and slight hemorrhage within

TM; 3 = gross hemorrhage within TM; 4 = hemotympanum; 5 = perforation of TM) were documented on every patient. The rate of compression change was constant for all participants (0.15 atmospheres absolute per minute). Patient education about methods to equalize ear pressure and not succumbing to "peer pressure" (and thus not declaring inability to equalize) when other patients were in the multiplace hyperbaric chamber was standardized for every enrollment. Patients unable to equalize ear pressure during compression were given oxymetazoline nasal spray as rescue therapy. The need to pause compression for the use of oxymetazoline was documented. We documented the reason why the study participant could not achieve compression. Pain ratings at target or maximum pressure tolerated were collected. Teed scores were documented on every patient after treatment upon exiting the chamber (by the same physician that performed the pre-treatment Teed evaluation). We considered severe pain as >7/10 or requiring abortion of HBO2 treatment.

Statistical analysis

Our comparisons were based on our primary outcome measures (pain ratings, Teed scores, and oxymetazoline rescue therapy) between placebo and pseudoephedrine. Our sample size, based on power 0.8, significance 0.05, and effect size 8% versus 32%, was 42 patients in each group. The effect size was based on barotrauma measured in SCUBA divers [10]. Initial allocation was 1:1, but by the 42nd enrollment, we learned that the capsules prepared by the investigational drug pharmacy required additional dissolution time, necessitating a 45-minute wait rather than the original 30-minute protocol. Because of inadequate time for drug effect, patients assigned pseudoephedrine up to that point were not considered for the primary outcome comparison. Thus, we subsequently changed our allocation to 2:1 to increase the number receiving pseudoephedrine, starting with subject #43. This increased our total enrollment from 84 to 105.

For comparisons of placebo versus pseudoephedrine, we used only subjects with pseudoephedrine ingested at least 45 minutes before HBO2 treatment. We used data from subjects provided pseudoephedrine less than 45 minutes before treatment only for estimates of the incidence of complications of HBO2 treatment.

We compared frequencies of primary outcome measures using chi-square or Fisher's exact test, as appropriate. We calculated 95% confidence intervals for the difference in frequencies between categories using normal binomial approximation. We compared ordinal variables using the Wilcoxon rank sum test.

We used logistic regression to adjust for potential confounding by baseline variables (age, sex, HBO2 pressure, history of obstruction, sinus disease, smoking, and inpatient status). We used backward selection, aiming for a precise and unbiased estimate of the pseudoephedrine effect. We removed only variables whose removal would not change this estimate by >10% or increase the standard error by >20%.

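### Only the normal-approximation interval is named for differences in frequencies: adequate at the design rates, but it can under-cover or shrink to zero width if an analysed outcome is rare

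*Combined protocol and SAP*

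**What the plan says.** Two sections of the combined protocol and SAP deal with this.

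- **Protocol, Statistical analysis.** The outcomes: "The primary outcome variable will be the frequency of severe pain and need for oxymetazoline rescue therapy, between the two groups". The test: "These frequencies will be compared using chi-square or Fisher's exact test, as appropriate". The interval: "We will calculate 95% confidence intervals for the difference in frequencies between groups using normal binomial approximation".
- **Materials and Methods, Statistical analysis** (from the accepted manuscript). The test: "We compared frequencies of primary outcome measures using chi-square or Fisher's exact test, as appropriate". The interval: "We calculated 95% confidence intervals for the difference in frequencies between categories using normal binomial approximation".

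The only event rates are those behind the sample size: "Our sample size, based on power 0.8, significance 0.05, and effect size 8% versus 32%, was 42 patients in each group". Both sections trace them to barotrauma in scuba divers. Enrollment (Materials and Methods) lists among its exclusions "history of hyperbaric treatment, SCUBA divers, those with pressure-equalizing tubes, and patients requiring emergent treatment". Neither section gives an expected rate for severe pain or for oxymetazoline rescue.

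**The concern.** The plan foresees sparse tables for the test but not for the interval. The normal-approximation (Wald) interval takes its standard error from the observed proportions. An arm with no events therefore contributes no variance, and the interval can be too narrow when events are few.

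At stake is how the size of effect is reported. If an outcome is rare and truly differs between arms, the Wald interval lies wholly below the true difference too often and so understates the possible benefit. If neither arm has an event, it is a single point at zero.

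**Working it through.** **Inputs.** 42 per group, alpha 0.05, power 0.80, 32% vs 8% (both Statistical analysis sections). Two-sided testing is assumed because the documents do not state sidedness. Every other rate below is an assumption.

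**1. The plan's own figure.** With pooled variance and no continuity correction, and mean rate 0.20:

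n = [1.96·√(2·0.20·0.80) + 0.8416·√(0.32·0.68 + 0.08·0.92)]² / 0.24² = (1.1087 + 0.4542)² / 0.0576 = 42.4

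That is 42 to the nearest integer and 43 rounded up. Power at 42 per group is 79.6%. The plan's figure is reproduced, and nothing here alters it.

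**2. The two intervals.** Write d = p1 - p2, placebo minus drug.

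- Wald: d ± 1.96·√[p1(1-p1)/42 + p2(1-p2)/42].
- Newcombe: lower limit d - √[(p1-l1)² + (u2-p2)²], upper limit d + √[(u1-p1)² + (p2-l2)²], where l and u are each arm's Wilson limits.

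**3. Coverage.** All 43 × 43 possible tables were enumerated, each weighted by its binomial probability.

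| True rates, placebo vs drug | Wald coverage | Newcombe coverage | Wald wholly below true difference (nominal 2.5%) | Mean width, Wald / Newcombe | Chance of no events on drug |
|---|---|---|---|---|---|
| 32% vs 8% (design) | 94.2% | 95.6% | 3.0% | 0.322 / 0.327 | 3.0% |
| 16% vs 4% | 94.2% | 96.1% | 4.2% | 0.246 / 0.273 | 18.0% |
| 10% vs 2.5% | 91.9% | 97.8% | 7.1% | 0.198 / 0.242 | 34.5% |
| 8% vs 2% | 93.9% | 98.5% | 5.3% | 0.177 / 0.229 | 42.8% |
| 5% vs 1.25% | 88.1% | 99.5% | 11.6% | 0.137 / 0.209 | 59.0% |
| 5% vs 5% | 95.4% | 98.4% | 2.3% | 0.178 / 0.231 | 11.6% |

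Wald coverage oscillates; it does not fall steadily as events become rarer.

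**4. Scans over the control rate, 2% to 40% in half-point steps (77 points).**

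- Design ratio of 4:1: Wald is below 95% at all 77 points, but stays within 92.9% to 94.7% once the control rate is 16% or more. It is below 93% at 16 points, 15 of them at control rates of 11% or less. The minimum, 65.1%, is at 2% vs 0.5%. Newcombe is at least 95.1% throughout. Wald is nevertheless the closer of the two to 95% at 23 points.
- Equal rates: Wald covers 94.0% to 99.1%; Newcombe's lowest value is 94.2%.

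**5. What the misses look like.**

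- At 10% vs 2.5% the true difference is 7.5 points. For 1/42 vs 0/42 the Wald upper limit is 0.0238 + 1.96·√(0.0238·0.9762/42) = 0.070, or 7.0 points, a near miss. Only 0.4% of intervals have an upper limit at or below zero.
- At 5% vs 1.25% that share is 6.9%, nearly all from tables with no events, which have probability (0.95·0.9875)^42 = 6.8%.

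**6. No events in either arm.** The Wald interval is 0 ± 0. The Wilson upper limit for 0/42 is 1.96²/(42 + 1.96²) = 3.84/45.84 = 0.084, so Newcombe gives -8.4 to +8.4 points.

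**The case against.** The strongest reply is that no error appears under the plan's own assumptions. At 32% vs 8%, Wald is 0.8 points from nominal and Newcombe 0.6, with nearly equal widths. That stands. Poor coverage is confined to low, unequal rates, and its worst value needs 0.84 and 0.21 expected events per arm (42 × 0.02 and 42 × 0.005). Newcombe is itself imperfect, being clearly conservative where Wald under-covers. Sparse tables can still be tested with Fisher's exact test, and ordinal variables are compared by Wilcoxon. All of this is correct and keeps the priority low. It does not supply an adequate interval for a sparse binary outcome.

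A further objection is that the analysis is finished, and replacing a pre-specified method once the data are known has a cost of its own. That also stands, and it shapes the fix.

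Four stronger readings are tempting but unsupported:

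- *The outcomes are rare.* A reader might infer this because the rates come from divers and divers are excluded. That shows only that the rates come from a different population; it points in neither direction.
- *Wald always under-covers.* The equal-rate results show otherwise.
- *A 0/42 vs 0/42 result carries no information.* It does: Newcombe bounds the difference at about 8 points either way. The fault of the 0% to 0% interval is that it claims far more precision than that.
- *Disagreement with Fisher's test proves Wald wrong.* At 4/42 vs 0/42 Wald gives +0.6 to +18.4 points while Fisher's p is 0.116. Such conflicts come mainly from Fisher's conservatism and are not a reason for the change.

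**Conclusion.** The concern holds in conditional form. Only the Wald interval is specified for a difference in frequencies. At the design rates it is adequate. If severe pain or rescue is rare and differs between arms, coverage can drop to about 92% (10% vs 2.5%) or 88% (5% vs 1.25%), and a table with no events yields a zero-width interval. These rates are assumptions, because the documents give none for these outcomes; the calculation also assumes 42 analysed per arm. The point concerns interval reporting only. It does not touch the sample size or the primary test, and it does not show that any reported interval is wrong. It is a low-priority improvement.

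**What to change.** In the protocol's Statistical analysis section, name the Newcombe (Wilson-score) interval for differences in binary outcomes. In the Materials and Methods section, where the analysis is complete, recalculate from the 2×2 counts, show the Newcombe interval beside the pre-specified Wald interval, and state that it was added after the fact.

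This takes one phrase and a short recalculation, with no new data. If the counts are moderate the intervals will barely move. The price is wider, conservative intervals for rare outcomes: at 5% vs 1.25%, mean width rises by about half (0.209/0.137 = 1.53). The gain is protection against under-coverage and zero-width intervals, not uniformly better coverage.
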